4.3 PHARMACOKINETICS POPULATION

The PK Population will include any subject who receives a dose of active Scop HBT and has at least one blood draw to determine the concentration of scopolamine in plasma or one urine sample to determine concentration in urine. All PK analyses will be performed on this population. Please note, the calculation of PK parameters will not be described or performed within this SAP. A separate PK manual and the report will detail the procedures, results, and limitations for the PK parameters.

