- **AUC_{∞}** : The area under the plasma concentration versus time curve from time 0 to infinity. AUC_{∞} is calculated as the sum of AUC_{last} plus the ratio of the last measurable plasma concentration to the elimination rate constant (k_e). The elimination rate constant will be determined from the terminal linear phase of the plasma concentration time profile.
- **$C_{max}/Dose$** : Dose normalization of C_{max} for evaluation of dose proportionality.
- **$AUC_{\infty}/Dose$** : Dose normalization of AUC_{∞} for evaluation of dose proportionality.

The terminal elimination phase is used to estimate a number of PK parameters. No value for V_d/F , Cl/F , AUC_{∞} , or $t_{1/2}$ will be reported for cases that do not exhibit a terminal log-linear phase in the concentration versus time profile. The PK analyses will not include the placebo group.

Outlier screens will first be carried out. For each PK parameter a one-way, heterogeneous variance analysis will be carried out across dose groups. Studentized residuals (i.e. residuals divided by their standard errors) will be calculated within each group and combined across groups. Studentized residuals in excess of three in absolute value will be considered “tentative outliers”. The tentative outliers will be examined by Battelle to determine if they are due to testing errors or data entry errors. If so, they will be reported and omitted from subsequent analyses. If the tentative outliers are correctly determined they will be treated as outliers and subsequent analyses will be carried out both including and excluding the outlying values.

Table 6: Pharmacokinetic Blood Sample Deviation Windows

Target Time Point	Acceptable Sample Collection Time Point Range		
	Low-End Range	High-End Range	Window
2 min	1 min 50 s	2 min 10 s	20 seconds
5 min	4 min 40 s	5 min 20 s	40 seconds
10 min	9 min 30 s	10 min 30 s	60 seconds
15 min	14 min 15 s	15 min 45 s	60 seconds
20 min	19 min	21 min	2 minutes
30 min	28.5 min	31.5 min	3 minutes
1 h (60 min)	57 min	63 min	6 minutes
2 h (120 min)	114 min	126 min	12 minutes
4 h (240 min)	228 min	252 min	24 minutes
8 h (480 min)	465 min	495 min	30 minutes
12 h (720 min)	705 min	735 min	30 minutes
24 h (1440 min)	1425 min	1455 min	30 minutes
36 h (2160 min)	2145 min	2175 min	30 minutes
48 h (2880 min)	2865 min	2895 min	30 minutes

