6.3 HYPOTHESES AND DECISION RULES

As the objective of this study is to characterize the safety and tolerability of escalating doses of Scop HBT, three sets of safety endpoints will be compared statistically between placebo and active dosing groups. Some PK parameters will also be compared statistically across dose levels. Table 7 describes the hypothesis testing pre-specified in the statistical analysis.

The null hypothesis of no worse scores for Injection Site VAS (pain, itching, tingling, numbness); change in BPRS Score (6 hours, 48 hours, 8 days); change in DSST (48 hours, 8 days); and C-SSRS (SD 8) between dose levels of active Scop HBT and placebo will be tested statistically using a one-sided alternative of worse (higher for C-SSRS, VAS, and BPRS, lower for DSST scores for Scop HBT vs. placebo). Each dose level will be tested against the same placebo group (all participants receiving placebo). Methods for analysis of neuropsychiatric scales and injection site reactions are described in Sections 6.13.4 [6.14.6](#) and [6.14.8](#), respectively.

For PK parameters, variation across doses will be tested for T_{max} , $t_{1/2}$, V_d/F , Cl_F , and MRT against the null hypothesis of no difference across doses. A joint significance test (1 test per parameter) will be used.

Dose-proportionality will be tested using the dose-normalized parameters $C_{max}/Dose$ and $AUC_{\infty}/Dose$. A likelihood ratio test will be used for testing the joint null hypothesis of equivalence across all doses using a two-sided alternative. Each dose level will also be tested against the next dose level using a two-sided test. The methods for analysis and hypothesis testing are described in Section - [6.15](#). A total of 110 hypothesis tests will be performed. Procedures for multiple comparisons are detailed in Section [6.8](#).

Table 7: Pre-Specified Hypothesis Tests

Drug Characteristic	Null Hypothesis	Relevant Endpoints [Count]	Number of Comparisons Per Parameter	Total Number of Hypothesis Tests
Safety	Equivalence with Placebo	Injection site VAS (pain, itching, tingling, numbness) x (10-45 minutes, 1-5 hours, 8-48 hours) [12] Change in BPRS score from baseline (6 hours, 48 hours, SD 8) [3] Change in DSST scores from baseline (48 hours, SD 8) [2]	5 (Each dose level vs. Placebo)	90

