Safety	Equivalence with Placebo	C-SSRS (SD 8) [1] Change in DSST scores from baseline (48 hours, SD 8) [2] Proportion with lower raw DSST scores compared to baseline (48 hours, SD 8) [2]	1 (All dose levels vs. Placebo)	5
PK Dose-Equivalence	Equivalence across doses	T_{max} , $t_{1/2}$, V_d/F , MRT, Cl_F	1 Joint Test	5
PK Dose-Proportionality	Equivalence across doses	$C_{max}/Dose$ $AUC_{\infty}/Dose$	1 (joint test) 4 (each dose vs. next higher dose)	10
Total				110

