6.8 ADJUSTMENT FOR MULTIPLE COMPARISONS

Section [6.3](#) specifies the hypotheses to be tested in this Phase 1 trial of the safety and pharmacokinetics of IM injection of Scop HBT. Given the large number of hypothesis tests, the Benjamini-Hochberg method will be used to determine statistical significance. As this trial is exploratory, a relatively high false discovery rate (FDR), the proportion of significant findings that are spurious, will be used. For this study, the FDR will be set at 0.20. The choice of a high FDR prevents rejecting marginally significant findings, which may provide important information about the drug's safety and pharmacokinetic properties. With 110 tests and an FDR of 0.20, the threshold for statistical significance for the five lowest p-values will be 0.0018,

0.0036, 0.0055, 0.0073, and 0.0091. Statistical significance of tests will be noted using at the alpha = 0.05 level as well as through the Benjamini-Hochberg method. Study sponsors should note that one-in-five significant findings obtained through this process are expected to be spurious.

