6.14.7 Assessment of Cognitive Impairment

The DSST will be used to measure cognitive impairment due to Scop HBT. The raw score will be calculated from the difference in total number of trials attempted and the number of trials incorrect. Summary statistics for raw DSST scores (mean, median, min, max, standard deviation, 95% confidence intervals) will be presented over time by dose level. The proportion of individuals with declines in raw scores between baseline and 48 hours and baseline and Day 8 will be compared between active placebo and active Scop HBT using a Fisher's Exact Test. This test will be conducted once for all participants receiving active Scop HBT and all participants receiving placebo.

In addition, individual changes in DSST scores between baseline and 48 hours and SD 8 will be compared between each dosage cohort and placebo and for all active dosages and placebo. Equation 5 presents the model that will be used to compare DSST scores by cohort,

$$G(Y_i) = \beta_0 + \beta_1 \times I(D_i = 1) + \beta_2 \times I(D_i = 2) + \beta_3 \times I(D_i = 3) + \beta_4 \times I(D_i = 4) + \beta_5 \times I(D_i = 5) + \varepsilon_i \quad (5)$$

where $Y_{i,}$ is the change in DSST scores at 48 hours or SD 8, D_i is the dosage level for participant i ($1=0.005, 2=0.007, 3=0.011, 4=0.014, 5=0.021 \text{ mg/kg}$), β_0 is the change in DSST scores for placebo participants, and ε_i is the error term for each participant i . Wald tests will be used for the null hypotheses of no differences between active Scop HBT and placebo: $\beta_1 = 0, \beta_2 = 0, \beta_3 = 0, \beta_4 = 0, \beta_5 = 0$.

Equation 6 shows the model that will be used to test the null hypothesis of no differences between all levels of active Scop HBT compared to placebo

$$G(Y_i) = \beta_0 + \beta_1 \times I(D_i \in \{1,2,3,4,5\}) + \varepsilon_i \quad (6)$$

A Wald test will be used to test the null hypothesis that there are no significant differences in the change in DSST scores between active and placebo Scop HBT ($\beta_1 = 0$) in Eq. 6.

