6.15 PHARMACOKINETIC ANALYSES

6.15.1 Plasma Pharmacokinetics

The estimation of pharmacokinetic parameters of interest is not described within this SAP. A separate PK report will detail methods and limitations of the estimation of PK parameters. However, PK parameters will be analyzed as part of this SAP.

PK parameters will be assessed for homoskedasticity prior to modeling using ANOVA. For parameters that vary by orders of magnitude across dose groups, a logarithmic transformation will be carried out prior to testing for homogeneity of variance. Otherwise a likelihood ratio test for homogeneity of variance will be carried out on the untransformed PK values or on transformed values, as appropriate. The tests for homogeneity of variance will exclude outlying values. If there are significant differences ($p < 0.05$) in variances across dose groups, comparison of PK means across dose groups will be carried out based on a heterogeneous variance analysis of variance. Otherwise it will be carried out based on a homogeneous variance analysis of variance.

Dose-equivalency of five PK parameters (T_{max} , $t_{1/2}$, V_d/F , CL_F , MRT) will be tested using ANOVA. Models will adjust for sex of the subject. Equation 3 presents the model to be used for all ANOVA of PK parameters,

$$G(Y_i) = \beta_0 + \beta_1 \times I(D_i = 2) + \beta_2 \times I(D_i = 3) + \beta_3 \times I(D_i = 4) + \beta_4 \times I(D_i = 5) + \beta_5 \times Sex_i + \varepsilon_i \quad (8)$$

, where G is a link function (or identity), Y_i is the PK parameter of interest i , β_0 is the change in PK parameter for the placebo group, D_i is the dosage level ($1=0.005$, $2=0.007$, $3=0.011$, $4=0.014$, $5=0.021$ mg/kg), and ε_i is an error term each for participant i . Models will control for the sex of the participant. The significance of the difference in parameters by dose level will be tested using a likelihood ratio test for the joint null hypothesis: $H_0: \beta_1 = \beta_2 = \beta_3 = \beta_4 = 0$. If bootstrapping is used, a null distribution will be generated using an F-statistic, as described previously. For parameters where dose-proportionality is assessed, the equivalency of each parameter with the next higher dose level will be tested, using the null hypotheses:

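### SAP 6.15.1, Eq. 9: the fifth next-higher-dose null (β4 = β5) compares the top dose with the sex effect and should be deleted; the β0 definition and an equation reference also need correcting

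*SAP*

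**What the plan says.** Eq. 8 in SAP 6.15.1 is the model for all PK parameters. It has an intercept β0, indicators for dose levels 2 to 5 with coefficients β1 to β4, and a sex term with coefficient β5. Level 1 (0.005 mg/kg) has no indicator and is therefore the reference.

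For the two dose-normalised parameters the SAP then says: "For parameters where dose-proportionality is assessed, the equivalency of each parameter with the next higher dose level will be tested, using the null hypotheses". Eq. 9 gives these as β1 = 0, β1 = β2, β2 = β3, β3 = β4 and β4 = β5.

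The text under Eq. 8 says that β0 "is the change in PK parameter for the placebo group". Elsewhere the PK population is limited to "any subject who receives a dose of active Scop HBT" (SAP 4.3), and SAP 5.2.1 adds: "The PK analyses will not include the placebo group". The text also calls the model Equation 3. That number belongs to the F-statistic in SAP 6.10; the model is numbered 8.

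Table 7 in SAP 6.3 budgets, for each of Cmax/Dose and AUC∞/Dose, one joint test plus "4 (each dose vs. next higher dose"). The same section states: "A total of 110 hypothesis tests will be performed". SAP 6.8 bases its significance thresholds on that count: "With 110 tests and an FDR of 0.20".

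**The concern.** Five active doses have four adjacent pairs, yet Eq. 9 lists five nulls. Under the coding of Eq. 8 the fifth involves the sex coefficient. A programmer who follows Eq. 9 literally would report, for each of two parameters, a sex-dependent result under a dose-proportionality label. Dose proportionality of Cmax and AUC∞ is part of the second study objective (SAP 2), and SAP 5.3 expects sex to matter for plasma PK, so the sex coefficient cannot be presumed to be zero. The wrong description of β0 adds to the confusion, because it suggests a model coding that the PK analysis does not use.

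**Working it through.** **Meaning of each line of Eq. 9 under two codings.** The left reading is Eq. 8 as printed. The right reading is the coding of Eq. 5, the DSST model in SAP 6.14.7, where β0 "is the change in DSST scores for placebo participants" and β1 to β5 are the five active doses.

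| Line | Under Eq. 8 | Under the coding of Eq. 5 |
|---|---|---|
| β1 = 0 | 0.005 vs 0.007 | placebo vs 0.005 |
| β1 = β2 | 0.007 vs 0.011 | 0.005 vs 0.007 |
| β2 = β3 | 0.011 vs 0.014 | 0.007 vs 0.011 |
| β3 = β4 | 0.014 vs 0.021 | 0.011 vs 0.014 |
| β4 = β5 | (0.021 minus 0.005) vs sex effect | 0.014 vs 0.021 |

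Neither coding makes all five lines valid. Under Eq. 8 the fifth fails. Under the coding of Eq. 5 the first fails: placebo is outside the PK analysis, and a dose-normalised value at dose zero is undefined. The five lines and the β0 wording both fit the coding of Eq. 5, so a carry-over from that model is plausible, though that is inference. The SAP does not say which sex is coded 1. Swapping the coding reverses the sign of β5 and changes the fifth null.

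**Test count.** Table 7 row totals: 90 + 5 + 5 + 2 × (1 + 4) = 110, which reproduces the stated total. With Eq. 9 as written: 90 + 5 + 5 + 2 × (1 + 5) = 112.

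**Benjamini-Hochberg thresholds (i × 0.20 / m).**
- m = 110: first 0.20/110 = 0.00182; fifth 5 × 0.20/110 = 0.00909. These agree with SAP 6.8 (0.0018 and 0.0091).
- m = 112: first 0.20/112 = 0.00179; fifth 5 × 0.20/112 = 0.00893.

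**What the fifth test does when exposure is exactly dose-proportional.** Inputs: 6 or 9 active subjects per dose (SAP 3.4), five doses, and a two-sided test at 0.05 (SAP 6.3 and 6.8). Assumptions: normal errors with equal variance, sexes as balanced as possible in each dose, a t reference with N − 6 degrees of freedom, and a sex effect in residual SD units, because the documents give no PK variance or sex effect size.

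Standard error of the β4 − β5 estimate, in residual SD:
- 6 per dose (3 and 3 by sex): √(2/6 + 4/30) = √0.4667 = 0.683
- 9 per dose (5 and 4 by sex): √(2/9 + 1/(5 × 20/9)) = √(0.2222 + 0.0900) = 0.559

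Rejection rates of β4 = β5 from 20,000 simulated data sets per row, with all true dose effects zero:

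| Assumed sex effect (SD) | 6 per dose | 9 per dose |
|---|---|---|
| 0 | 0.05 | 0.05 |
| 0.5 | 0.11 | 0.14 |
| 1.0 | 0.29 | 0.42 |
| 1.5 | 0.56 | 0.75 |

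The four valid nulls stay at about 0.05 throughout. The fifth test can also miss a real departure. If the top dose and sex effects are both +1 SD, it rejects about 5% of the time, while the valid contrast β3 = β4 rejects 38% (6 per dose) or 54% (9 per dose).

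**The case against.** The strongest reply is that this is an editorial slip with an obvious intention. Table 7 gives four adjacent tests per parameter, SAP 6.3 and 6.8 both work from 110 tests, SAP 6.15.1 says the dose-normalised parameters are compared across active doses, and the top dose has no next higher dose. A careful programmer would drop the line. SAP 6.1 also says the objectives are addressed mainly by descriptive statistics, and SAP 6.8 calls the trial exploratory.

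Most of this stands. It settles what was meant and keeps the consequence small. It does not make the fifth null valid, and Eq. 9 is the explicit instruction that would be programmed.

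A reader might go further and infer that the joint likelihood-ratio tests are anti-conservative because a chi-square reference is inaccurate at these sample sizes. The documents do not support that. No section names a chi-square reference, and SAP 6.10 gives an F-statistic with a resampled null for the same joint hypothesis. SAP 6.15.1 ties the F-statistic to the bootstrap, so the reference without bootstrapping is unstated. That is missing detail; it does not show an inflated error rate.

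A reader might also see an unresolved conflict over unequal variances, since Protocol 12.5 names robust standard errors and the SAP names a heterogeneous-variance ANOVA. SAP 1 says the SAP prevails where the two differ, so the method is settled and only its degrees of freedom are unstated.

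**Conclusion.** The point holds as a small, certain error in the SAP text. Under Eq. 8, β4 = β5 is not a next-higher-dose contrast, β0 is not the placebo group, and the model is Equation 8. These follow from the equations alone and need no assumption.

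The consequence is limited to one invalid, mislabelled result for each of Cmax/Dose and AUC∞/Dose, and a count of 112 against 110. The 29% and 42% rejection rates depend on an assumed sex effect of 1 residual SD; with no sex effect the rate is the nominal 5%.

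It would be wrong to conclude that the dose-proportionality analysis is lost or its multiplicity control upset. All four valid contrasts are in Eq. 9, and the thresholds barely move. Escalation is unaffected: Protocol 12.3 and SAP 6.7.2 say the DSMB uses no statistical test to decide whether to halt or terminate the study.

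**What to change.** In SAP 6.15.1:

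- Delete β4 = β5 from Eq. 9. Four nulls remain, giving 2 × (1 + 4) = 10 dose-proportionality tests and 110 in all, as in Table 7.
- Define β0 as the mean of G(Y) at 0.005 mg/kg in the reference sex, and state which sex that is.
- Change the reference from Equation 3 to Equation 8.

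The cost is one deleted line and two wording corrections before unblinding. Protocol 12.1.1 asks for each dose against the next higher one, and that is kept in full, so no protocol-specified analysis changes.

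Optional clarification, separate from the error: for normal linear models with equal variances and no bootstrap, state that the joint likelihood-ratio test is referred to its equivalent F distribution. With five doses and sex in the model, LR = N × ln(1 + 4F/(N − 6)), which increases with F, so the protocol's likelihood-ratio test is kept and F(4, N − 6) is its exact reference.

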6.15.2 Urine Pharmacokinetics

The analysis of urine PK is exploratory and descriptive only. If available, urine concentrations and total quantities of Scopolamine in urine will be summarized by collection time window for each cohort. If metabolites of Scopolamine are analyzed, their concentrations and the ratio of Scopolamine to its metabolites will be calculated and presented descriptively as a function of collection window and dosing group. No hypothesis testing will be performed based on urine PK.

REFERENCES

None at this time.

Tables, Listings, and Figures

See separate shell document.

6.16 LIST OF TABLES

See separate shell document.

6.17 LIST OF LISTINGS

See separate shell document.

7. APPENDICES

None at this time.
